5. STUDY OBJECTIVES

The objectives of this study are to describe the safety and immunogenicity of ALVAC-HIV (vCP205) administered via 2 alternative delivery routes in an effort to improve the immunogenicity of this vaccine candidate as defined by improved cellular immune responses. It is a Phase I description of the acute safety and immunogenicity of ALVAC-HIV (vCP205) transfected autologous DC, or ALVAC-HIV (vCP205) delivered by the intradermal route. The internal referent will be the standard method of delivery via the intramuscular route. This will be the first study of vCP205 delivered ID or via autologous dendritic cells in HIV-seronegative humans.

6. INVESTIGATIONAL PLAN

6.1 Overall Study Design and Plan

This will be a phase I study in 36 low-risk, HIV-1 seronegative U. S. volunteers. The study is divided into three groups, all to describe safety and immunogenicity. In Group I, 12 volunteers will be given ALVAC-HIV (vCP205) transfected autologous dendritic cells pulsed with KLH (4 of these will receive KLH pulsed DC only) as a means of directly targeting these cells to enhance the immunogenicity of the vaccine. All four immunizations with the DC-vCP205 vaccines will be generated from the same initial leukopheresis blood cell product. DC precursors can be cryopreserved and prepared before each vaccination. In Groups II and III, 12 volunteers in each group, will be immunized with the exact same type of vaccine in current use, ALVAC-HIV (vCP205), but given by different routes (intradermal or intramuscular). Four volunteers will be given placebo (sterile saline) by the ID route and 4 volunteers by the IM route. In essence, we plan to describe the immune responses with directly injected ALVAC-HIV into the skin or muscle and ALVAC-HIV transfected DC injected into the subcutaneous space. All volunteers (all groups) will undergo leukopheresis before vaccination and 2 weeks after the final vaccination. Cells derived from the leukopheresis are crucial for establishing the dendritic cells for arm I of the study but will also be used to characterize and compare the immune responses against HIV within and between all three study arms. The advantage of the apheresis is that the large number of cells will permit comparison of novel CTL assays systems to accepted gold standard procedures and allow for the characterization of the sensitivity, specificity and reproducibility within and between arms. This pheresis process safely provides many more white blood cells than can be obtained from a routine venipuncture with minimal red blood cell loss. A new test for West Nile diagnosis was recently instituted in the WRAMC blood bank. All blood donors are required to have their blood tested for this infection. This may affect some volunteers in this trial, although no additional blood is drawn. It may be added to the list of routine blood tests already performed as part of the blood bank screening process.

This study will provide new, preliminary data regarding the respective immunogenicities of intradermal and *ex vivo* DC immunization with vCP205 relative to the moderately immunogenic IM route in normal human volunteers. The study is not designed to resolve the null hypothesis.

			Months			
Group	Vaccine/	Subcutaneous	0	1	3	6
	Placebo*	Route				
Ι	8/4	DC	DC-vCP205 KLH pulsed or KLH pulsed DC only	DC-vCP205 or DC only	DC-vCP205 or DC only	DC-vCP205 or DC only

Subcutaneous Administration of vCP205 via transfected, autologous dendritic cells

Vaccine = vCP205 transfected DC pulsed with KLH, *Placebo = DC pulsed with KLH only (control DC) delivered in 2 x 0.2 ml subcutaneous injections. The KLH is used in the first vaccination only. $vCP205 = \sim 10^{6.5} \text{ TCID}_{50} (1 \text{ vial})$ reconstituted in1 ml sterile water/ 2-3 x 10^{6} DC

Intradermal or Intramuscular Administration of vCP205 via injection

			Months			
Group	Vaccine/ Placebo ¹	Route	0	1	3	6

II	8/4	Intradermal	vCP205	vCP205	vCP205	vCP205
III	8/4	Intramuscular	vCP205	vCP205	vCP205	vCP205

 $ID = \sim 10^{6.5} TCID_{50} (1 \text{ vial})$ reconstituted in 1 ml sterile water, delivered in 4 x 0.125 ml intradermal injections (0.5 ml total dose).

 $IM = \sim 10^{6.5} TCID_{50}$ (1 vial) reconstituted in 1 ml sterile water, delivered in a single 1 ml intramuscular injection (1.0 ml total dose).

 1 Placebo = sterile saline

6.2 Rationale for the Study Arms:

Group I. Delivery of ALVAC-HIV vCP205 to autologous *ex vivo* generated DC. We will directly target the dendritic cell as a means of maximizing the antigen presentation of encoded HIV-1 genes within the vaccine vector. Theoretically, this arm would serve as the optimal antigen delivery method in this descriptive study. It will provide important conceptual information on the benefits of directly loading critical antigen presenting cells with vectors for HIV vaccine development. If the results indicate beneficial effects of directly targeted-DC, this type of study will lay the groundwork for future vaccine development with an emphasis on *in vivo* DC targeting. We will include the use of KLH as a control antigen in this arm (for the first injection only) as means of quality control to ensure that the canarypox transfection process is not inhibitory for DC function in some way. We can then reasonably use the anti-KLH (primary) immunity that would develop in the control DCs as an internal referent for this arm.

Group II. We propose to optimize the immunogenicity of this vaccine and augment the cellular immune response against HIV immunogens by using different methods of delivery. Other pox vaccines delivered intradermally have induced broader immune responses when compared to intramuscular delivery. ^{34,68} Some vaccines are specifically recommended to be given intradermally for optimal immune responses, eg rabies, hepatitis and cholera vaccines ³¹⁻³³. The intradermal delivery of vaccines may directly access the skin-dwelling antigen presenting cell compartment and facilitate *in vivo* targeting. Additionally, intradermal delivery allows the use of lower doses of certain vaccines while inducing the same or better immune response ^{31,34a-c}. Since this study was designed to evaluate the potential for improved immunogenicity of the existing vaccine candidate vCP205, we chose to administer as much of the vCP205 vaccine as feasible by the ID route. We are attempting to improve the immune response to the vaccine and will give a comparable dose using a reasonable number of injections. Intradermal vaccines are limited by the volume that can be delivered into the intradermal compartment, approximately 0.1-0.15 ml per injection. We plan to give 4 x 0.125 ml ID injections for each of the vaccinations which will deliver one-half of the IM dose (i.e. 0.5 ml ID vs. 1.0 ml IM).

Group III. ALVAC-HIV vCP205 has been previously tested in humans (intramuscular route) and found to be apparently safe and moderately immunogenic. This arm evaluates the response to vCP205 given in the usual IM route as an internal referent. Responses to this vaccine in humans are well characterized and will establish the external validity and generalizability of this study and provide a means of reference to the existing standard vaccine delivery system.

6.3 Assessment of Immunogenicity

6.3.1 Primary Measures of Immunogenicity--All Subjects

Immunogenicity: Description of the following primary measures of cellular immunogenicity

• Lymphocyte proliferation responses to specific vaccine component antigens (which includes gp160 MN/LAI protein from Aventis Pasteur and p24 LAI protein from MicroGeneSys) and to the control antigen KLH (for DC arm only).

• Cytotoxic T-lymphocyte (CTL) responses against vaccine component antigens expressed in a recombinant poxvirus vector system (expressing HIV env MN antigen, gag and pol LAI antigens) in standard bulk chromium release assays.

• ELISPOT analysis for gamma-interferon production from bulk PBMCs in response to vaccine antigen stimulation (or other relevant antigens as they become available) in an overnight culture system.

• Enumeration and characterization of antigen specific gamma-interferon production using flow cytometry

6.3.2 Ancillary Immunogenicity Studies

Measurement of breadth of antibody response by characterizing

-serum binding and neutralizing antibody to vaccine component antigens, including anti-ALVAC antibodies (ELISA)

-anti-KLH binding antibodies (ELISA) in dendritic cell arm only

-neutralizing antibody activity against primary isolates in vaccinee sera that display high level of neutralizing activity against the HIV-1 MN strain.

Measurement of breadth of cellular response by quantifying and characterizing

- modified bulk CTL assay using autologous dendritic cells for in vitro stimulation

- identification of selected cytokine/chemokine production from supernatants from LPA

- mapping of cross-reactive cellular epitopes by measuring lymphocyte proliferation and CTL activity against proteins and/or peptides from diverse HIV-1 subtypes.

6.4 Selection of Study Populations

The total study population consists of 36, healthy low-risk HIV-1 seronegative U.S. adult volunteers from the community and can include civilians or DOD dependents. Subjects will be 18 through 55 years of age (< 10% will be > 50 years old). Subjects should not be engaging in highest risk behavior for HIV (i.e., injection drug use or sex with HIV positive partner). Women must agree to practice effective contraception for 60 days prior to study entry and until 6 months after the fourth immunization. Subjects will be followed up for 6 months after the fourth immunization and will then have their study termination visit according to the protocol schedule of events. Volunteer recipients who experience HIV-1 infection during the trial or up to 18 months after the last immunization, will be offered enrollment in a study to evaluate the "natural history" of HIV-1 occurring in vaccine recipients, if eligible and referred to a local physician for follow-up health care.

6.4.1 Inclusion Criteria:

Volunteers are eligible for this study if they meet all the following criteria:

1. Legal residents of USA who are not at high-risk for HIV infection.

2. Age: 18 to 55.

3. For women, a valid negative serum pregnancy test prior to vaccination will be required, as well as verbal assurance that adequate birth control measures are applied 60 days prior to the first vaccination and for 6 months after the final vaccination.

4. Good health as determined by medical history, physical examination, and clinical judgment.

- 5. Clinical laboratory values at screening within the following normal ranges:
 - Hematocrit: Women: 35 % to 45 %; Men 36 % to 49 %

- White cell count: 3,000 to 10,800 cells/mm³

- Platelets: 150,000 to 400,000 per mm³

6. Urinalysis for protein and blood: negative or trace. If either is $\geq 1+$, repeat the UA. If evidence of blood or protein on repeat UA (microscopic and repeat dipstick) is confirmed, the volunteer is ineligible and will be appropriately referred for diagnosis and treatment.

7. Normal ALT (<1.5x institutional upper normal limit) and creatinine (0.1 - 1.6 mg/dL)
8. Negative serology for HIV infection (ELISA test), HIV RNA below detection limits of FDA approved viral load diagnostic assay.

9. Availability for at least 15 months of participation.

10. Successful completion of the Test of Understanding (maximum of 3 attempts to pass the test). Commitment for Trial Participation and signature of the approved consent form.

11.Successful EBV transformation of subjects B-cells obtained at the minus 90 to 30 day screening visit. If first attempt at EBV transformation is unsuccessful, a second attempt (blood draw) can be made. Subject is enrolled into study only if the EBV transformation is successful. A modified screening evaluation (that will include screening labs) will be repeated if greater than 12 weeks prior to date of enrollment. The EBV-transformation step is critically important because these transformed cells are required for the CTL assay, which allows the investigators to monitor the cellular immune response to the vaccine.

6.4.2 Exclusion Criteria:

Individuals will not be enrolled into the study if they meet at least one of the following criteria:

1. Acknowledge engaging in highest-risk behavior within 6 months of study entry: (e.g., active injecting drug use or having sexual intercourse with a known HIV-1 infected partner).

2. Have active tuberculosis or other systemic infectious process by review of systems and physical examination.

3. Have a history of significant cardiac arrythmias (ventricular tachycardia or ventricular fibrillation), seizure disorder, immunodeficiency, chronic illness, autoimmune disease, diabetes mellitus (Type I or II pre-existing diagnosis, or random glucose ≥ 200 or fasting plasma glucose ≥ 126 - see diagnostic criteria in the report: Expert Committee on the Diagnosis and Classification of Diabetes Mellitus *Diabetes Care* Vol 25, Suppl 1, Jan 2002) or use of immunosuppressive medications.

4. Have evidence of psychiatric, medical and/or substance abuse problems during the past 6 months that the investigator believes would adversely affect the volunteer's ability to participate in the trial. 5. Have occupational or other responsibilities that would prevent completion of participation in the study.

6. Have received any live attenuated vaccine within 60 days of study entry.

NOTE: Medically indicated subunit or killed vaccines (e.g., Hepatitis A, Hepatitis B or rabies) are not exclusionary but should be given at least 2 weeks before, or 2 weeks after, HIV immunizations to avoid potential confusion of adverse reactions. However, if rabies vaccine is indicated in the post-exposure setting, it will take priority over the study vaccine.

7. Have used experimental therapeutic agents within 30 days of study entry.

8. Have received blood products or immunoglobulins in the past 3 months.

9. Have a history of anaphylaxis or other serious adverse reactions to vaccines.

10. Have previously received an HIV vaccine.

11. Are pregnant or breastfeeding.

NOTE: Women of child-bearing potential must be using effective contraception for at least 60 days prior to initial vaccination and for at least 6 months after the final vaccination.

12. Have chronic or active hepatitis B or Hepatitis C virus infection or active syphilis (positive RPR and FTA).

13. Have an immediate type hypersensitivity reaction to eggs, egg products or neomycin (used to prepare ALVAC vaccine) or gentamicin (used in preparation of the DC).

14. Are study site employees who are involved in the protocol and may have direct access to the immunogenicity results.

15. In the event that we are unable to generate autologous dendritic cells (DC) in sufficient quality or quantity from a volunteer who is randomized to the DC arm (Group I)-that volunteer will be excluded.

6.4.3 Removal of Subjects from Trial or Assessment

A subject may withdraw his/her consent to participate in the study at any time without prejudice. Additionally, the investigator may withdraw a subject if, in his/her clinical judgment, it is in the best interest of the subject or if the subject cannot comply with the protocol. Wherever possible, the tests and evaluations listed for the termination visit should be carried out if the subject refuses follow-up according to the protocol visit schedule. The sponsor should be notified of all study withdrawals within 24 hours. Subjects who withdraw from the study will be replaced only as long as the study is still open for enrollment. No replacement will be allowed when the enrollment is closed.

Obtaining Replacement Vial Assignment: If a subject withdraws from the study and is to be replaced, the principal investigator/study coordinator must contact DCAC to receive a replacement number. Replacement will only be permitted during the active enrollment phase. A fax or telephone message must be sent to DCAC providing the subject identification number of the withdrawn participant.

All subjects who receive at least one immunization will be included in the safety analysis. Only subjects who have received four injections and have had the Visit 11 blood draw (2 weeks post-fourth immunization) will be included in the final immunogenicity analysis, though immunogenicity data may be used in the analysis of earlier timepoints. If a subject misses an immunization visit (i.e., visit 4 or 7), no further immunizations will be performed, but the subject will continue to be followed according to the protocol visit schedule. If a subject misses a non-immunization visit (i.e., visit 3 or 5), immunization will continue as planned. A missed visit is defined as outside the allowed window for each visit. If a subject does not complete the immunization schedule secondary to a serious adverse event or toxicity, he or she will continue to be followed according to the protocol visit schedule, and, at a minimum, until the adverse event/toxicity is resolved and/or the cause is identified.

A genuine effort will be made to determine the reason(s) why a subject fails to return for the necessary visits. If the subject is unreachable by telephone, a registered letter, at the minimum, will be sent to the subject requesting contact with the clinic. This information will be recorded on the appropriate source document. For subjects who become pregnant before completing the vaccine series, no further immunizations will be given regardless of outcome. The subject will be followed for all remaining scheduled visits according to the schedule of procedures for safety evaluation. For all subjects who become pregnant while participating in the trial, a Pregnancy CRF will be completed. The site will maintain contact with pregnant subjects to obtain pregnancy outcome information for the Pregnancy Follow-up CRF (See Appendix 17.4).

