Route of Administration: *Ex vivo* generated and transfected, autologous dendritic cells will be injected into the subcutaneous tissue of the upper arm with a tuberculin syringe. Vaccine via intradermal injection will be injected into the dermis of the volar skin of the forearm. Intramuscular injections will be administered into the deltoid muscle of the arm.

IMMUNIZATION SCHEDULE

Subcutaneous Administration of vCP205 via transfected, autologous dendritic cells

			Months			
Group	Vaccine/	Subcutaneous	0	1	3	6
	Placebo*	Route				
Ι	8/4	DC	DC-vCP205	DC-vCP205	DC-vCP205	DC-vCP205
			KLH pulsed	or	or	or
			or	DC only	DC only	DC only
			KLH pulsed	-	-	
			DC only			
			-			

Vaccine = vCP205 transfected DC pulsed with KLH, *Placebo = DC pulsed with KLH only (control DC) delivered in 2 x 0.2 ml subcutaneous injections. The KLH is used in the first vaccination only. vCP205 = $\sim 10^{6.5}$ TCID₅₀ (1 vial) reconstituted in 1 ml sterile water/ 2-3 x 10⁶ DC

Intramuscular or Intradermal Administration of vCP205 via injection

			Months			
Group	Vaccine/	Route	0	1	3	6
	Placebo*					
II	8/4	Intradermal	vCP205	vCP205	vCP205	vCP205
III	8/4	Intramuscular	vCP205	vCP205	vCP205	vCP205

 $ID = \sim 10^{6.5} TCID_{50}$ (1 vial) reconstituted in 1 ml sterile water, delivered in 4 x 0.125 ml intradermal injections (0.5 ml

total dose). IM= $\sim 10^{6.5}$ TCID₅₀ (1 vial) reconstituted in 1 ml sterile water, delivered in a single 1 ml intramuscular injection (1.0 ml total dose).

¹Placebo = sterile saline

STUDY ENDPOINTS

Safety and Tolerability: Tabulation of adverse effects and laboratory abnormalities: All subjects will be observed for 1 hour following immunizations for evidence of immediate local and systemic reactions. They will be instructed to watch for local and systemic reactions for 7 days post-immunization and will be evaluated by an investigator if significant symptoms are reported. Routine measurements of hematology, serum chemistry, and urinalysis laboratory tests will be performed 14 days after each vaccination.

Immunogenicity: Description of the following primary measures of immunogenicity.

Lymphocyte proliferation responses to specific vaccine component antigens

(which includes gp160 MN/LAI protein from Aventis Pasteur and p24 LAI protein from MicroGeneSys) and to the control antigen KLH (for DC arm only).

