-samples of the final product will be sent for mycoplasma culture immediately prior to vaccination. Reasons to **hold** the product will be a positive Gram stain or positive 48hr. culture result, evidence of endotoxin, evidence of mycoplasma contamination or DC viability less than 70%. Identity must be completely tracked and verified with documentation. Other tests will be performed but results will not be a hold issue. These are detailed in **Appendix A**.

If a volunteer is justifiably vaccinated outside a window, all subsequent visits will be scheduled in reference to that most recent vaccination. For example, if the vaccination visit is 6 weeks late, the safety visit will still occur 2 weeks after that vaccination. All subsequent vaccination intervals will occur as originally planned in the protocol and consequently the schedule will just shift. Justifiable vaccinations given outside a window may be due to manufacturing or production issues or severe scheduling constraints outside the investigators' or volunteers' control. An important aspect of the scheduling for DC vaccinations is that the schedule is already quite constrained as we generally only give DC injections on Wednesdays or Thursdays. This is because of all the release testing that is required for a DC injection. Also, it takes one week to prepare a DC vaccine; compared to the other routes (IM or ID) which can be given anytime simply by taking the vaccine off the "shelf". The combination of a long preparation time and restricted vaccination days make out of window events more likely to occur in this arm. These out of window events due to manufacturing issues, etc are to be distinguished from the compliance ranges specified in the Section 6.4.3 Removal of Subject form Trial."

Group II. Aventis Pasteur ALVAC-HIV (vCP205) $\sim 10^{6.5}$ TCID₅₀ reconstituted in1 ml of sterile water. - Recombinant Canarypox that expresses (*env/gag/pro*) HIV genes Supplied as lyophilized product, reconstituted in 1.0 ml sterile water and given as 4 x 0.125 ml intradermal injections for a total dose of 0.5 ml. (Please note the ID dose is one-half the IM dose).

Group III. Aventis Pasteur ALVAC-HIV (vCP205) $\sim 10^{6.5}$ TCID₅₀ reconstituted in 1 ml of sterile water. - Recombinant Canarypox that expresses (*env/gag/pro*) HIV genes Supplied as lyophilized product, reconstituted in 1.0 ml sterile water and given as a single 1 ml intramuscular injection (for a total dose of 1.0 ml).

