1. Obtain interim history and physical including vital signs and abbreviated risk assessment.

2. Perform serum pregnancy test for women before immunization.

Results of pregnancy test must be known prior to vaccination.

3. Collect samples for immunogenicity (40 ml anticoagulated blood): LPA, neutralizing antibody, CTL and ELISPOT. Separately and additionally, draw 3 ml of blood into a heparinized pediatric tube (no substitutions) PRIOR to immunization (whole blood ICC).

4. Collect archival blood specimen (10 ml of anticoagulated blood).

5. Administer vaccine injection(s) into the left deltoid muscle (IM), or the volar aspect of the left arm (ID). The autologous DC are prepared from the pre-study leukopheresis. The DC are checked for sterility and identity and after being cleared for release, injected into the superficial subcutaneous space on the ventral inner aspect of the left arm in two 0.2 ml aliquots. Examine the injection sites for local reactions at 60 minutes post-injection for all injections and instruct subject in the evaluation of these local reactions; observe and instruct while the subject takes temperature (as guided for subsequent evaluations); enter findings on appropriate CRF.

6. Subjects will record daily symptoms for 7 days post-immunization (including the day of immunization), and will be instructed to contact the investigator if any untoward effects occur.

24-48 hour contact after the second immunization:

Subjects will be contacted by staff within 24 to 48 hours post-immunization (by telephone, by home visit, or by the other prearranged mechanism) to determine whether adverse effects have occurred. Subjects will be queried using a predetermined review of systems/reactogenicity worksheet. If the adverse effects experienced by the volunteer are deemed "moderate", he/she will be asked to return to clinic for evaluation by the investigator. Additional contacts will be arranged as indicated.

Visit 5: Day 42 after initial vaccination, 14 days (+/-4 days) after second vaccination: Safety Evaluation

1. Collect diary, obtain interim history and physical.

2. Collect sample for CBC.

3. Collect sample for Chem-7, LFT's (Na, K, Cl, HCO3, Cr, BUN, Glc, AST, ALT, Total Bili, alk phos).

4. Collect urine for dipstick. If urine protein or blood is 1+ or greater, obtain a complete UA.

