5. Collect sample for cellular immunogenicity assays (40 ml of anticoagulated blood): LPA, CTL and ELISPOT. Separately and additionally, draw 3 ml of blood into a heparinized pediatric tube (no substitutions) PRIOR to immunization (whole blood ICC).

6. Collect archival blood specimen (10 ml of anticoagulated blood).

Visit 6: Day 60 after initial vaccination, 32 days (+/-7 days) after second vaccination

1. Obtain interim history including vital signs and abbreviated risk assessment.

2. Collect blood for autoimmunity tests (ANA, Rheumatoid factor, and anti-thyroid antibodies), 2 ml red top.

3. Collect samples for immunogenicity (40 ml anticoagulated blood): LPA, neutralizing antibody, CTL and ELISPOT.

Visit 7: Third Vaccination, Day 90 (+/- 14 days) after initial vaccination

1. Obtain interim history and physical including vital signs and abbreviated risk assessment.

2. Collect samples for HIV serology (1 ml red top).

3. Perform serum pregnancy test for women before immunization.

Results of pregnancy test must be known prior to vaccination.

4. Administer vaccine injection(s) into the left deltoid muscle (IM), or the volar aspect of the left arm (ID). The autologous DC are prepared from the pre-study leukopheresis. The DC are checked for sterility and identity and after being cleared for release, injected into the superficial subcutaneous space on the ventral inner aspect of the left arm in two 0.2 ml aliquots. Examine the injection sites for local reactions at 60 minutes post-injection and instruct subject in the evaluation of these local reactions; observe and instruct while the subject takes temperature (as guided for subsequent evaluations); enter findings on appropriate CRF.

5. Subjects will record daily symptoms for 7 days post-immunization (including the day of immunization), and will be instructed to contact the investigator if any untoward effects occur.

24-48 hour contact after the third immunization:

Subjects will be contacted by staff within 24 to 48 hours post-immunization (by telephone, by home visit, or by the other prearranged mechanism) to determine whether adverse effects have occurred. Subjects will be queried using a predetermined review of systems/reactogenicity worksheet. If the adverse effects experienced by the volunteer are deemed "moderate", he/she will be asked to return to clinic for evaluation by the investigator. Additional contacts will be arranged as indicated.

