6.6.2.2 Stopping Criteria

A severe adverse event or grade III/IV toxicity which is probably or definitely related to vaccination will result in discontinuation of vaccination for the individual. The volunteer will be asked to continue the follow-up schedule for the duration of the study.

Two severe adverse events or grade III/IV toxicity which are probably or definitely related to vaccination will result in discontinuation of the study arm. The volunteers will be asked to continue the follow-up schedule for the duration of the study.

Discontinuation of a study arm will prompt an immediate analysis of study safety data for all arms, a review of available immunogenicity data and consideration of modifying the design of the discontinued study arm (i.e.dose reduction) to minimize the risks to participants in the modified arm. New volunteers would be recruited for the modified study arm.

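### After a missed Day 14 safety visit the next dose still goes ahead, so the Grade III/IV stopping rule may be applied with no post-vaccination laboratory data

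*Protocol*

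**What the plan says.** Section 6.4.3 treats missed visits in two ways. A missed immunization visit ends further dosing. For other visits: "If a subject misses a non-immunization visit (i.e., visit 3 or 5), immunization will continue as planned". A visit counts as missed when it falls outside its window.

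Section 6.6.2.2 sets the individual stopping rule: "A severe adverse event or grade III/IV toxicity which is probably or definitely related to vaccination will result in discontinuation of vaccination for the individual". Two such events stop the arm. Section 6.6.2.3 counts laboratory changes as adverse events, and the scale in Section 18.6 grades haematology, chemistry and urine values.

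The Protocol Summary, under Study Endpoints, gives the laboratory timing: "Routine measurements of hematology, serum chemistry, and urinalysis laboratory tests will be performed 14 days after each vaccination". In Section 6.5.6 these tests fall at Visits 3, 5, 8 and 11. At the later dosing visits (4, 7 and 10) the listed precondition is the pregnancy test: "Results of pregnancy test must be known prior to vaccination". Visit 6, on Day 60, has one safety blood item: "Collect blood for autoimmunity tests (ANA, Rheumatoid factor, and anti-thyroid antibodies), 2 ml red top".

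**The concern.** The visits whose absence is declared no obstacle to dosing are the ones that supply the laboratory half of the stopping rule. A symptom-free Grade III or IV change in, say, transaminases, neutrophils, platelets or creatinine can be seen only if blood is drawn. If it is not drawn, a volunteer who meets the individual criterion can be dosed again, and the event does not yet count towards the two that stop the arm.

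Section 5 describes the setting: "This will be the first study of vCP205 delivered ID or via autologous dendritic cells in HIV-seronegative humans". Between-dose laboratory safety data carry particular weight in a study of that kind.

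**Working it through.** The plan states no figure to reproduce. The check traces which visits supply CBC, chemistry and urine results between consecutive doses, then measures the time available for a late draw.

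**Inputs (Section 6.5.6).** Nominal doses fall on Days 0, 28, 90 and 180. Safety tests are at Visit 3 (Day 14), Visit 5 (Day 42), Visit 8 (Day 104) and Visit 11 (Day 194), each within 4 days of the fourteenth day after the dose. Dose windows are 28 ± 7, 90 ± 14 and 180 ± 14 days.

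**Post-vaccination results available at each dose, assuming no late draw**

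- No visit missed: dose 2 has Visit 3, dose 3 has Visit 5, dose 4 has Visit 8.
- Visit 3 missed: dose 2 has none. The first result comes on Day 42, after 2 of 4 doses.
- Visit 5 missed: dose 3 has nothing from after dose 2.
- Visits 3 and 5 both missed: doses 2 and 3 have none. The first result comes on Day 104, after 3 of 4 doses.

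The visits in between do not fill the gap. Visits 4, 7 and 10 list no CBC, chemistry or urine test and no review of earlier safety results. Visit 6 draws autoimmunity and immunogenicity samples, and the autoantibodies are not in the grading scale.

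**What goes unmeasured (Section 18.6 against the Visit 3 and 5 panels).** Haematology 5 (assuming the CBC includes a differential) + chemistry 8 (sodium, potassium, creatinine, glucose, AST, ALT, bilirubin, alkaline phosphatase) + urine 2 (protein, blood) = 15 parameters. About 27 clinical rows remain observable.

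**Time for a late draw.** Days available = close of next dose window − close of safety-visit window. For the DC arm subtract 7, because "it takes one week to prepare a DC vaccine" (Section 6.5.1).

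| Next dose | Safety window closes | Dose window closes | Days | DC arm |
|---|---|---|---|---|
| 2 | 14 + 4 = 18 | 28 + 7 = 35 | 17 | 10 |
| 3 | 28 + 14 + 4 = 46 | 90 + 14 = 104 | 58 | 51 |
| 4 | 90 + 14 + 4 = 108 | 180 + 14 = 194 | 86 | 79 |

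These margins use the last day of each dose window. The tightest case is dose 2 on its first permitted day: 21 − 18 = 3 days. In the DC arm, a dose 2 on Day 28 means preparation starts on Day 21, also 3 days after Visit 3 closes.

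**Frequency, as illustration only.** Let *m* be the chance that a Visit 3 or 5 passes with no draw before the next dose. This is assumed, and taken as independent across 36 × 2 = 72 visits. The expected number of doses given without prior laboratory data is 72*m*, and the chance of at least one is 1 − (1 − *m*)^72.

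- *m* = 2%: 1.4 expected, 77%.
- *m* = 5%: 3.6 expected, 98%.
- *m* = 10%: 7.2 expected, over 99%.

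These count doses given without laboratory data, in vaccine and placebo recipients together. They do not count toxicities missed.

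**The case against.** The sentence in Section 6.4.3 can be read as a retention rule: missing a safety visit is not in itself a reason to end dosing. It does not override Section 6.6.2.2 or forbid a late draw. Because a missed visit is defined by its window, a volunteer seen on Day 19 with full tests has technically missed Visit 3 and is properly dosed.

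Other text helps. Section 6.4.3 asks for a genuine effort to find out why volunteers fail to return, and it lets the investigator withdraw a volunteer. Section 11 asks that every attempt be made to obtain the requested data. The Protocol Summary plans preliminary safety analyses after doses 1 and 2. Clinical monitoring also continues, with the 60-minute observation, the 24 to 48 hour contact, the diary, and history and physical at dosing visits. The background is reassuring: no serious event was attributed to ALVAC in over 1500 seronegative recipients, and over 100 patients given DC had no significant acute toxicity.

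The evidence has limits too. The Section 6.7 flow chart cannot be read here. The Section 6.5.6 lists may be incomplete, since Section 6.6.1 schedules Day 14 cellular samples that Visit 3 does not list.

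All of this lowers the likely frequency of harm, but none of it closes the gap. No provision requires a make-up draw or holds a dose until results are seen, and a preliminary analysis cannot include tests that were never drawn. Section 12 classes missed scheduled visits as minor deviations, reported in summary with the annual review. On laboratory timing, the Protocol Summary independently agrees with the visit lists.

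**Conclusion.** The concern holds for the laboratory part of the stopping rule only. The protocol expressly lets dosing continue after a missed Visit 3 or 5, and nothing else it schedules replaces the CBC, chemistry and urine results before the next dose. At worst, three of four doses precede the first post-vaccination result, with about 15 graded parameters unmeasured.

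Harm requires a missed visit, no late draw, and a symptom-free Grade III/IV abnormality judged probably or definitely related. That combination is probably rare, but the documents do not allow its frequency to be estimated. The conclusion rests on the Section 6.5.6 visit lists and assumes the unreadable flow chart adds no further tests. It is a worthwhile safety correction at small cost, and it does not undermine the design.

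**What to change.** - **Section 6.4.3:** after a missed safety visit, immunization continues only once the preceding dose's CBC, chemistry and urine tests, drawn late if necessary, have been reported and graded against Section 6.6.2.2.
- **Section 6.5.6, Visits 4, 7 and 10:** list that check beside the pregnancy result. This also covers dose 4, since Visit 8 is a non-immunization visit too, although Section 6.4.3 does not name it.
- **Late samples:** after a missed Visit 5 use Visit 6, and after a missed Visit 8 use Visit 9. Both already draw blood. After a missed Visit 3, arrange one extra contact before dose 2. In the DC arm, draw and grade before preparation starts.
- **Section 6.5.1:** the current exception reads "Justifiable vaccinations given outside a window may be due to manufacturing or production issues or severe scheduling constraints outside the investigators' or volunteers' control". Add a short hold for outstanding safety results as a further accepted reason. Otherwise a dose held past its window would end dosing under Section 6.4.3 and drop the volunteer from the final immunogenicity analysis, a loss of 1/8 = 12.5% of an arm's active recipients.

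The cost is one amended sentence, one check line at three visits and one added reason. The late sample (3 ml CBC, 3 ml chemistry, urine) replaces one already planned. An occasional dose will be delayed. This matters most in the DC arm, where preparation takes a week and injections are generally confined to two weekdays. A draw about a month after dosing, at Visit 6 or 9, may miss a transient abnormality that Day 14 would show, so an earlier late draw is better where the volunteer can attend.
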